7.9.3.3. Total insulin dose

The mean insulin total daily delivery dose will be calculated from pump data uploaded in CareLink Clinical at visits: 5 (randomization, week=0-1), 6 (week=0), 7 (week=1), 9 (week=6), 11 (week=12), 13 (week=18) and 15 (week=24). Summary statistics for quantitative variables will be reported at every visit.

7.9.3.4. HbA1c level and number of sensor hypoglycemia events per week by subgroups

Summary statistics for (quantitative variables) will be reported for HbA1c level and for the mean number of sensor glucose hypoglycemic events per subject per week (sensor glucose values of ≤ 55 mg/dL (3.0 mmol/L)) by study arm and by:

- Age group
 - o Grouping A. group 1: age < 65 , group 2: Age ≥ 65
 - o Grouping B. group 1: age $<$ median age, group 2 \geq median age.
- Duration of diabetes
 - o Grouping A. group 1: < 10 years, group 2 ≥ 10 years
 - o Grouping B. group 1: < 20 years, group 2 ≥ 20 years
 - o Grouping C. group 1: < 30 years, group 2 ≥ 30 years
- Duration of pump therapy at time of screening
 - o Grouping A. group 1: $<$ median duration of pump therapy, group 2 \geq median duration of pump therapy
- Baseline HbA1c
 - o Grouping A. group 1: Baseline HbA1c $< 6\%$, group 2: Baseline HbA1c $\geq 6\%$
 - o Grouping B. group 1: Baseline HbA1c $< 7\%$, group 2: Baseline HbA1c $\geq 7\%$
 - o Grouping C. group 1: Baseline HbA1c $\leq 7.5\%$, group 2: Baseline HbA1c $> 7.5\%$
 - o Grouping D. group 1: Baseline HbA1c $< 8\%$, group 2: Baseline HbA1c $\geq 8\%$
 - o Grouping E. group 1: Baseline HbA1c $< 9\%$, group 2: Baseline HbA1c $\geq 9\%$
- Baseline type of insulin
 - o group 1: Lispro (Humalog), group 2: Aspart (Novolog), group 3: Glulisine (Apidra) and group 4: Other

7.9.3.5. Mean weight

The mean weight will be reported for screening (Visit 2) and end of study phase (Visit 15). Summary statistics for quantitative variables will be reported at every visit.

7.10. Safety Evaluation

Safety analysis will include Number of severe hypoglycemic events, diabetic ketoacidosis events, (Serious) Adverse Events, (Serious) Adverse Device Effects and Device Deficiencies.

Analysis will include: hypoglycemia-related number and mean duration of hospitalizations, number and mean duration ICU (intensive care unit) care, number of emergency room admissions, number of events requiring ambulance assistance and number of lost days from school or work.

7.10.1. Number of severe hypoglycemic events

A severe hypoglycemic event is an event *requiring* assistance of another person due to altered consciousness to actively administer carbohydrate, glucagon, or other resuscitative actions. This means that the subject was impaired cognitively to the point that he/she was unable to treat his or her self, was unable to verbalize his or her needs, and was incoherent, disoriented and/or combative. These episodes may be associated with sufficient neuroglycopenia to induce seizure or coma. Plasma glucose measurements may not be available during such an event, but neurological recovery attributable to the restoration of plasma glucose to normal is considered sufficient evidence that the event was induced by a low plasma glucose concentration.

Total number of severe hypoglycemic events, reported as SAEs in the eCRF, during Run-In (Visit 1 to before Visit 5) and Study Phase will be reported. Total number of severe hypoglycemic events during the Study Phase (from date of Visit 5 to date of Visit 15) will be reported by treatment arm.

The number of severe hypoglycemic events per year will be computed for each subject based on the entire study phase duration (happening after Visit 5 to and including Visit 15). If a subject is followed up for x months and the number of observed severe hypoglycemic events during that follow up is m , the number of severe hypoglycemic events per year ($SHEyear$) for that patient will be estimated as:

$$SHEyear = \frac{12}{x} m$$

Annualized crude incidence rates will be expressed as number of severe hypoglycemic events per 100 patients' year and will be computed following these steps: First, the average of the number of severe hypoglycemic events per year is calculated as

$Mean_{(SHEyear)} = \sum_{i=1}^n SHEyear_{(i)} / n$, where $i = 1, 2, \dots, n$ and n total number of subjects. This represents the mean number of severe hypoglycemic events per year in a subject. Second, the number of severe hypoglycemic events per 100 patients' year is calculated as $100 * Mean_{(SHEyear)}$.

The number of severe hypoglycemic events per 100 patients' year will be calculated and reported by study arm.

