	J.2.2 Potential risks associated with the use of the GST3C Transmitter	63
	J.2.3 Potential risks associated with the use of other investigational devices	63
	J.2.4 Potential risks associated with the use of MiniMed 640G Insulin pump:	63
	J.2.5 Potential risks associated with the use of SmartGuard Feature	64
	J.2.6 Potential risks associated with the use of CONTOUR NEXT LINK 2.4 meter	64
J.3	Risk-to-benefit rationale	64
K	REFERENCES.....	65
L	APPENDICES.....	66
L.1	Names and addresses	66
	L.1.1 List of contact persons	66
L.2	Case Report Forms	67
L.3	Sample Investigator Agreement	67
L.4	List of consumables	67
L.5	Sample Questionnaires	68
L.6	Abbreviations	69

FIGURES

Figure 1: Study design overview	15
Figure 2: Medtronic MiniMed 640G insulin pump	20
Figure 3: Enlite 3 Sensor and One-Press serter	21
Figure 4: GST3C Transmittte and GST3C Charger	21
Figure 5: CONTOUR NEXT LINK 2.4 meter	21
Figure 6: CareLink USB 2	22
Figure 7: Watertight Tester	24
Figure 8: Study design overview	36

TABLES

Table 1 Study procedures and data collection	15
Table 2 Clinical evidence SAP therapy with SmartGuard	17
Table 3: Number of devices per subject	24
Table 4 Summary of glycemic recommendations for non-pregnant adults with diabetes	34
Table 5: Study procedures and Data collection	37
Table 6 Adverse Event Reporting Requirements	52

A SYNOPSIS

Title

SMILE - Study of MiniMed™ 640G Insulin Pump with SmartGuard™ in prevention of Low Glucose Events in adults with Type 1 diabetes (CEP311).

Purpose

The aim of the study is to evaluate the efficacy of sensor augmented pump (SAP) therapy with MiniMed™ 640G and SmartGuard™ in preventing hypoglycemic events in comparison with continuous subcutaneous insulin infusion (CSII) therapy in type 1 diabetes adults with an increased risk of hypoglycemia.

Design

A pre-market, multi-center, prospective, open label, adaptive, randomized controlled study.

Medical device/product

The following CE-marked products will be provided during the course of the study:

- MiniMed™ 640G Insulin Pump (MMT-1711,mmol/L) or (MMT-1712,mg/dL).
Subjects already using a MiniMed™ 640G pump will not be provided with a pump for the purpose of this study and will continue using their own pump.
- CareLink™ USB 2 (MMT-7306)
- CareLink™ Clinical Therapy Management Software version 5.1 (MMT-7334) or subsequent versions
- MiniMed™ Quick-set™, MiniMed™ Mio™, MiniMed™ Silhouette™, MiniMed™ Sure-T™ and MiniMed™ Mio™ 30 infusion sets (detailed list in appendix L.4).

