- Mean Time spent of sensor glucose values within range and including 70-140 mg/dL (3.9 -7.8 mmol/L) and 70-180 mg/dL (3.9-10.0 mmol/L) and categorized by starting at daytime (08:01 to 21:59) and night-time (22:00 to 08:00).

C.2.2.5 HbA1c

- Mean HbA1c change from baseline to 6 months and stratified by baseline HbA1c level $\leq 7.5\%$ and $>7.5\%$.

C.2.2.6 Sensor glucose values surrounding SmartGuard events

- Mean sensor glucose values surrounding SmartGuard triggered insulin suspensions lasting <30 , ≥ 30 to <90 , and ≥ 90 to 120 minutes. Mean sensor glucose values 60 min before and up to 360 min after suspend before low is activated categorized by suspensions lasting less than 30, ≥ 30 to <90 , ≥ 90 to 120 minutes, and categorized by starting at daytime (08:01 to 21:59) and night-time (22:00 to 08:00).
- Proportion of Suspend before low events that reached the pre-set Low Limit calculated, as per the individualised Low Limit settings at any given time point.

C.2.2.7 Change in glycemic variability

- Excursion amplitudes of the glucose values measured by mean amplitude of glycaemic excursions (MAGE), 24-hour standard deviation (SD) of glucose values.

C.2.3 Tertiary endpoints / descriptive analysis:

These will include and are not limited to the following (and described in the Statistical Analysis Plan):

- Safety endpoints: Number of severe hypoglycemic events, diabetic ketoacidosis events, (Serious) Adverse Events, (Serious) Adverse Device Effects and Device Deficiencies (see F.6 for definitions).
- Hypoglycemia-related number and mean duration of hospitalizations, number and mean duration of ICU care, number of emergency room admissions, number of events requiring ambulance assistance and number of lost days from school or work.
- HbA1c level and mean number of sensor glucose hypoglycemic events per week will be reported by age groups, duration of diabetes, duration of pump therapy at time of screening, type of insulin analog used in study
- Mean number of SMBG
- Mean Clarke, Gold, HFS and DTSQ questionnaires scores.
- Mean Weight and mean insulin total daily delivery dose.

C.3 Study Hypothesis

The primary study hypothesis is described as follow:

Mean number of sensor glucose hypoglycaemic events below or equal to 55 mg/dL (3.0 mmol/L) per patient/week (MNSHE) will be calculated in the TREATMENT arm (SAP with MiniMed 640G and SmartGuard) and the CONTROL arm (CSII with MiniMed 640G) and will be compared using the next hypotheses:

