Medtronic	Immediately after the investigator first learns of the event or of new information in relation with an already reported event.
Regulatory Authority	As per local reporting requirement.
EC/IRB	Submit to EC/IRB per local reporting requirement.
Sponsor submit to:	
Regulatory Authorities	Reporting timeframe as per local requirement.
EC/IRB	Submit to EC/IRB per local reporting requirement.
Adverse Device Effects (ADE)	
Investigator submit to:	
Medtronic	Immediately after the investigator first learns of the event.
Regulatory Authority	As per local reporting requirement.
EC/IRB	Submit to EC/IRB per local reporting requirement.
Sponsor submit to:	
Regulatory Authorities	Reporting timeframe as per local requirement
EC/IRB	Submit to EC/IRB per local reporting requirement.
All other AEs	
Investigator submit to:	
Medtronic	Submit in a timely manner after the investigator first learns of the event.
Regulatory Authority	As per local reporting requirement.
EC/IRB	Submit to EC/IRB per local reporting requirement.
Device Deficiency with SADE potential	
Investigator submit to:	
Medtronic	Immediately after the investigator first learns of the deficiency or of new information in relation with an already reported deficiency.
Regulatory Authority	As per local reporting requirement.
EC/IRB	Submit to EC/IRB per local reporting requirement.
Sponsor submit to:	
Regulatory Authorities	Reporting timeframe as per local requirement
EC/IRB	Submit to EC/IRB per local reporting requirement.
All other Device Deficiencies	
Investigator submit to:	
Medtronic	Submit in a timely manner after the investigator first learns of the deficiency.
Regulatory Authority	As per local reporting requirement.
EC/IRB	Submit to EC/IRB per local reporting requirement.
Sponsor submit to:	
Regulatory Authorities	Reporting timeframe as per local requirement
EC/IRB	Submit to EC/IRB per local reporting requirement.

F.6.6 Clinical events Committee

An independent Clinical events Committee (CEC) consisting of external physicians with an expertise in endocrinology and the management of diabetes, including insulin pumps and CGM will be convened. The CEC will review all reports of:

- Serious Adverse Event (SAE)
- Serious Adverse Device Effect (SADE)
- Unanticipated Adverse Device Effect (UADE)
- Severe Hypoglycemia
- Severe Hyperglycemia
- Diabetic Ketoacidosis (DKA)
- Death

The responsibilities of an CEC committee are:

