- Review all reported SAE, SADE, UADE, Severe Hypoglycemia, Severe Hyperglycemia, DKA and deaths, and determines event classification (e.g. seriousness, severity, relatedness to device and procedure, unanticipated/anticipated) on a periodic basis.
- Upon request advise Sponsor about the potential clinical impact of an observed unintended device performance.
- Advise Sponsor in cases of SADEs.

A CEC charter will be established to indicate explicit rules outlining the minimum amount of data required and the algorithm followed in order to classify/adjudicate an event.

The CEC will assess these events to determine agreement or disagreement with the Investigator classification of the event. CEC decisions will be documented in meeting minutes. The Sponsor will notify the Investigator of any disagreement in assessment of an event by the CEC.

All other events will be reviewed and classified by the Sponsor's qualified internal safety individual(s) to ensure they should not be adjudicated by the CEC and that the events are appropriately classified by the investigator.

F.6.7 Data Safety Monitoring Board

The purpose of a data monitoring committee is to protect the safety of trial participants, the credibility of the study and the validity of study results. An independent Data Safety Monitoring Board (DSMB) will reassess the study sample size at the moment of the planned interim analysis.

The DSMB is established by the sponsor to oversee the following responsibilities:

- Review the interim analysis of effectiveness and safety measures after 60 subjects(30 treatment and 30 control group) have been randomized and followed up for 6 months.
- Following predefined rules in the DSMB chart, implement the assessment of modifications to the trial design.
The primary planned modification is a sample size re-estimation.
- Monitor baseline comparability.
- Monitoring adverse events: review aggregate subject data.
- Provide recommendations to continue or terminate the trial depending upon these analyses.

F.6.8 Emergency contact details in case of serious AEs

In case of an immediately reportable Adverse Event the investigators can contact the Medtronic study manager. Should the team members change during the course of the study, you may contact the current study manager.

F.7 Subject accountability

Subjects who are unwilling to participate in the follow up visits or complete study procedures should be withdrawn.

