7.10.2. Number of severe hyperglycemic events

A severe hyperglycemic event is defined as hyperglycemia (blood glucose >300 mg/dL) with blood glucose ketones >0.6mmol/L or accompanied by symptoms of nausea, vomiting or abdominal pain

Total number of severe hyperglycemic events, reported as SAEs in the eCRF, during Run-In (Visit 1 to before date of Visit 5) and Study Phase will be reported. Total number of severe hyperglycemic events during the Study Phase (from date of Visit 5 to date of Visit 15) will be reported by treatment arm.

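### The SAP takes severe hypo- and hyperglycaemia totals from the eCRF and names no source for DKA; neither document says that the independent committee's classification enters the analysis or prevails.

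*SAP*

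**What the plan says.** The Protocol synopsis describes the trial as "A pre-market, multi-center, prospective, open label, adaptive, randomized controlled study". Protocol C.2.3 lists these events among the tertiary, descriptive endpoints: "Safety endpoints: Number of severe hypoglycemic events, diabetic ketoacidosis events, (Serious) Adverse Events, (Serious) Adverse Device Effects and Device Deficiencies".

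Protocol F.6.6 sets up "An independent Clinical events Committee (CEC) consisting of external physicians with an expertise in endocrinology" and diabetes management. Its first task is: "Review all reported SAE, SADE, UADE, Severe Hypoglycemia, Severe Hyperglycemia, DKA and deaths, and determines event classification". The examples of classification given there are seriousness, severity, relatedness and anticipation. A charter is to hold the adjudication algorithm. Decisions are recorded in meeting minutes, and for a difference of opinion the text provides that "The Sponsor will notify the Investigator of any disagreement in assessment of an event by the CEC".

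On the analysis side, SAP 7.10.1 reports "Total number of severe hypoglycemic events, reported as SAEs in the eCRF, during Run-In" and the study phase, then a study-phase total by arm and an annualised rate per 100 patient-years by arm. SAP 7.10.2 has the parallel wording: "Total number of severe hyperglycemic events, reported as SAEs in the eCRF, during Run-In". SAP 7.10.3 (DKA) and 7.10.4 (SAEs, serious adverse device effects (SADEs) and device deficiencies) give definitions and say counts will be reported, without naming a data source. The available SAP text does not mention the CEC or adjudication, either in its abbreviation list or in 7.12, where departures from the protocol are explained.

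**The concern.** The trial will produce two classifications of the same events: one by site staff who know the allocation, and one by external physicians applying charter rules. The SAP points to the record that the site completes and the investigator signs, and it is silent about the other.

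The choice matters most for severe hypoglycaemia, because its definition calls for judgement. Someone has to decide whether another person's help was needed because of altered consciousness, and a glucose value may be missing. In an open-label comparison of a device meant to prevent hypoglycaemia, that judgement is exposed to knowledge of the arm. If the two classifications differ, the counts by arm and the annualised rate depend on which is tabulated. A choice left open until the data are in can be made after both sets of counts are known.

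**Working it through.** The point is mainly textual, and the plan has no figure of its own to reproduce. The passages line up as follows.

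1. **Who classifies.** Protocol F.6.6: the CEC, for all reported events of the three types as well as SAEs, SADEs, unanticipated device effects and deaths. Investigators make their own assessment on the Adverse Event eCRF (F.6.3).
2. **Where each classification is held.** Investigator: the eCRF, signed by physicians at the site (G.1.1.1). CEC: meeting minutes (F.6.6). No eCRF field or analysis dataset for CEC decisions is named.
3. **What happens on disagreement.** The sponsor notifies the investigator (F.6.6). No rule says which view prevails for analysis.
4. **What the SAP counts.** Severe hypo- and hyperglycaemia: events entered as SAEs in the eCRF (7.10.1, 7.10.2). The sentences on by-arm totals and the annualised rate name no other source, so the natural reading is that they use the same one. DKA: no source (7.10.3).
5. **Whether this was a declared change.** SAP 7.12 explains several departures from the protocol; setting adjudication aside is not among them.

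DKA has an added reason to need a named classifier. Protocol F.6.2 gives a diagnostic list that includes pH, bicarbonate and anion gap, then a recording list that accepts either pH or bicarbonate. SAP 7.10.3 repeats the diagnostic list. An event recorded under one list may not meet the other, and the SAP does not say who decides.

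**Sensitivity to one event.** This needs no assumed event rate.

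- Inputs: 160 randomised 1:1, so 80 per arm (Protocol C.7, SAP 6.2); study phase 168 days (SAP 7.7.1); up to 14 days between Visits 5 and 6 (Protocol F.3.6); rate = 100 × mean over subjects of (12/x)·m, with x months of follow-up and m events (SAP 7.10.1).
- One event in a subject followed for 168 days: x = 168/365 × 12 = 5.52 months; 12/5.52 = 2.17; 100 × 2.17/80 = 2.7 per 100 patient-years.
- If Visit 5 falls the full 14 days before Visit 6: 182 days, x = 5.98; 100 × (12/5.98)/80 = 2.5.
- One event in a subject who leaves after one month (illustrative): 100 × 12/80 = 15.

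Adding or removing one event changes the between-arm difference by the same amount, since the other arm does not move.

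**The case against.** The strongest reply is that silence does not prove site classifications are what will be tabulated. A reader might infer that an event the CEC rejects must stay in the analysis as the site entered it. The documents do not establish that. Protocol F.6.1 has the sponsor classify each adverse event under ISO 14155 for the clinical report. G.1.3 provides for queries, and G.1.1.1 for changes to signed eCRFs with re-signature and an audit trail. A CEC disagreement could therefore lead to a corrected eCRF, and the SAP wording could describe that corrected database. The CEC charter, Data Management Plan and table templates are separate documents and may say more. This stands, and it limits the point to what can happen under the text as written.

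Three further limits also stand.

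- A reader might infer that DKA, SAEs and SADEs are counted from site classifications too. SAP 7.10.3 and 7.10.4 name no source, so for those events the gap is silence.
- A reader might treat the CEC label as blinded. F.6.6 makes the committee independent but does not say it is masked to arm. It also reviews only reported events, so it cannot repair differential under-reporting.
- The CEC's listed examples do not expressly include whether an event meets the severe hypoglycaemia definition. The list is illustrative, however, and seriousness, which is on it, bears directly on a count of events entered as SAEs.

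What does not stand is that the SAP merely omits detail. For severe hypo- and hyperglycaemia it names a source, and that source is not the CEC's classification.

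**Conclusion.** The point holds as a gap between the two documents. The Protocol plans an independent classification of these events. The SAP names the eCRF for two of the three types and nothing for the third, and no rule carries the CEC's decision into the analysis. The descriptive by-arm counts and the annualised severe hypoglycaemia rate can therefore rest on unblinded site classification where the CEC disagreed.

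The consequence is modest. The events are tertiary endpoints outside the testing hierarchy of SAP 7.5, and SAP 7.10 specifies no between-arm test. The primary endpoint and the sample size are untouched. The documents give neither an expected event rate nor a disagreement rate, so neither the number of affected events nor the direction of any bias can be derived. The single-event shift of about 2.5 to 2.7 per 100 patient-years assumes 80 subjects in the arm and a subject who completes on schedule. It shows how far one decision moves the reported rate and does not forecast how many decisions will differ.

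The change is worth making because the better source is already planned and costs little to use. It is separate from whether counting should be limited to events flagged as SAEs: lifting that limit would still leave open whose classification is used.

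**What to change.** - **SAP 7.10.1 to 7.10.3:** state that by-arm counts and rates of severe hypoglycaemia, severe hyperglycaemia and DKA use the CEC's final classification, with investigator-reported counts and the number of disagreements shown beside them.
- **SAP 7.10.4:** state the same for the SAEs and SADEs that the CEC reviews.
- **Protocol F.6.6:** state that the CEC classification prevails for analysis, and name the dataset that holds it, since meeting minutes alone cannot feed a table.

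The CEC and its review are already planned, so the cost is wording, a data field or transfer for CEC decisions, and a delay: the counts are final only after the last CEC meeting. Removing the allocation from the review packet is optional, and the fix does not depend on it.

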DTSQc questionnaire														X	X	
AEs and Deficiencies																
Study deviations																

Reported upon occurrence or at a site visit and CareLink Clinical data upload, if possible.

¹ Visit 1-2, 2-3, 1-2-3 can be combined; ² Visit 5-6 can be combined; ³ O = Optional. Only for subjects who did not have a recent test (see Visit 2: Screening for details); ⁴ T = Treatment arm; ⁵ C = Control arm; ⁶ Early Termination visit should be performed at any time if patient withdraws after randomization (Visit 5) and before the end of the study (Visit 15).

B GENERAL INFORMATION

B.1 Introduction

Managing type 1 diabetes requires constant vigilance and attention to diet, exercise, and insulin regimens, and depends on consistently delivering the right amount of insulin at the right time. Medtronic's insulin delivery systems have been helping type 1 diabetes patients with their diabetes management for more than 30 years. The insulin pump system is indicated for the continuous delivery of insulin, at set and variable rates, for the management of diabetes mellitus in persons requiring insulin. Technological advances in insulin pump delivery systems and key clinical trials have established the value of this therapy in helping patients with their daily diabetes management.

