6.2. Sample size

The sample size calculation was performed based on assumptions from the results of the *ASPIRE study* (Bergenstal, et al., 2013). In particular, the mean number of sensor glucose hypoglycemic events below or equal to 55 mg/dL (3.0 mmol/L) per subject/week is expected to be 2 with standard deviation of 1.65 in the Control arm (CSII therapy alone with MiniMed 640G).

Assuming a two-sided two-sample t-test, alpha=0.05, power=80% and 40% reduction in the mean number of sensor glucose hypoglycemic events per subject/week in the Treatment arm (SAP with MiniMed 640G and SmartGuard), as compared to the control arm, the required sample size is 136 subjects (68 in each arm) completing the 6 month follow up of the study phase.

The dropout rate during the 6-month follow-up after randomization has been estimated to be around 15%. Incorporating this dropout rate, a total of 160 subjects will be randomized in a 1:1 ratio either to the SAP therapy arm (MiniMed 640G with SmartGuard) or to the CSII therapy arm (MiniMed 640G).

7. Statistical Methods

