7.1.3.3. Safety set

Safety analysis will include all subjects with signed informed consent and safety data will be presented by phase (run-in phase and study phase). Safety reporting will be done separately for the run-in period and the study phase period. Any AE and SAE occurring from the date of Visit 1 to before the date of Visit 5 will be reported as happening in the run-in phase. Any AE and SAE occurring from the date of visit 5 to the date of Visit 15 will be reported as happening in the study phase and will be reported according to the randomization arm that the subject was assigned.

For comparison of safety in the two arms, the safety set is composed of all randomized subjects, and assessed and analyzed as members of the intended randomized arm.

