In each period, it is expected to have 4032 sensor readings, which are equivalent to 14 days of sensor data and represents 100% sensor usage. The mean number of hypoglycemic events per subject per week is calculated for each of the subjects in each of the periods (period1, period2 and period3) using the blinded (for control arm) or unblinded (for treatment arm) sensor data collected as indicated in section 7.7.2. With the available sensor readings, the number of hypoglycemic events will be calculated and expressed as events per week for each period for each subject. For example: If a subject has 1 sensor hypoglycemic events in 14 days (2 weeks) in a particular period, then the number of sensor glucose hypoglycemic events per week for that subject in that period is: (1 hypoglycemic event/ 2 weeks) = 0.5 hypoglycemic events/week. If a subject in a particular period has 2016 sensor readings (representing 50% sensor usage), which are equivalent to 1 week and 1 sensor hypoglycaemic event, then the number of sensor glucose hypoglycemic events per week for that subject in that period is: (1 hypoglycemic events / 1 week)= 1 hypoglycemic event/week.

Selection of sensor data: In case a subject has less than 3 days of sensor data (< 3*288 sensor points) during one of the periods of 2 weeks, then the mean number of hypoglycemic events/week for that subject in that period will be missing.

In case the MNSHE shows a Poisson like distribution, the transformation \sqrt{MNSHE} (and $\sqrt{BLMNSHE_i}$) may be considered for the mixed model as a sensitivity analysis.

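### The severe hypoglycemia rate in SAP 7.10.1 is called a crude incidence rate per 100 patient-years but is an unweighted mean of subjects' annualised rates, with no minimum follow-up

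*SAP*

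**What the plan says.** SAP 7.10.1 announces its output this way: "Annualized crude incidence rates will be expressed as number of severe hypoglycemic events per 100" patient-years, by study arm. The calculation has three steps.

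- Per subject: "If a subject is followed up for x months and the number of observed severe hypoglycemic events during that follow up is m", the annual rate is 12m/x.
- Across subjects: "First, the average of the number of severe hypoglycemic events per year is calculated as" the sum of these rates over n, the number of subjects. The SAP describes this average as a subject's mean yearly number of events.
- Scaling: the average is multiplied by 100.

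The section gives no lower limit for x and no weighting by follow-up. It also reports event totals by arm, but no total of patient-years.

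For the comparison between arms, SAP 7.1.3.3 states that "the safety set is composed of all randomized subjects". SAP 6.2 anticipates drop-out of about 15% after randomization. Footnote 6 to Protocol Table 1 provides for withdrawal at any point between Visit 5 and Visit 15.

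Other sections do have rules for short data. Under SAP 7.9.1, a subject with fewer than 3 days of sensor data in a period is set aside: "then the mean number of hypoglycemic events/week for that subject in that period will be missing". SAP 7.7.1 and 7.7.3 fix the denominators used for drop-outs when sensor wear and pump wear are calculated.

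**The concern.** A crude incidence rate per 100 patient-years means total events divided by total person-time. In that rate each subject counts in proportion to follow-up. In the SAP's average each subject counts equally, however short the follow-up. The two agree when follow-up is equal, but this plan expects it to be unequal.

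The weight that one event receives is 12/x, which grows without limit as x falls. At x = 0 (exit on the day of Visit 5) the subject's value is undefined.

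Severe hypoglycemia leads the safety endpoints listed in Protocol C.2.3, and the trial recruits people at raised risk of it. This is the only exposure-adjusted rate that the SAP specifies for the event, and it is shown by arm. A reader will take it as events over person-time and cannot recover that figure from the planned output. The trial is open-label, so drop-out could differ between arms, although the documents give no figure for this.

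**Working it through.** The SAP gives no numerical rate, so there is no figure to reproduce. The check compares two formulas on the planned arm size:

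- SAP statistic: 100 × (1/n) × Σ(12mᵢ/xᵢ)
- Person-time rate: 100 × Σmᵢ / (Σxᵢ/12)

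**Inputs from the SAP.** 160 randomized 1:1 gives 80 per arm (6.2). With 15% drop-out there are 68 completers and 12 leavers. A completer has 168 days (7.7.1) = 168/30.4375 = 5.52 months.

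**Contribution of one event to the sum (12/x).**

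| Follow-up x | 12/x | Relative to a completer |
|---|---|---|
| 5.52 months | 2.17 | 1 |
| 1 month | 12 | 5.5 |
| 0.5 month | 24 | 11 |
| 1 week | 52 | 24 |

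**Boundary case (assumed).** There are 68 completers, 11 leavers at a mean of 12 weeks (2.76 months), and one leaver at 0.5 month who has one event. A further k events fall in completers.

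Person-time = (68 × 5.52 + 11 × 2.76 + 0.5)/12 = 33.85 patient-years.

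| k | SAP: 100 × (24 + 2.174k)/80 | Person-time: 100 × (1 + k)/33.85 | Ratio |
|---|---|---|---|
| 0 | 30.0 | 2.95 | 10.2 |
| 3 | 38.2 | 11.8 | 3.2 |
| 10 | 57.2 | 32.5 | 1.8 |

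If the arm's only event is instead in a subject leaving at week 8, the SAP gives 100 × (52.18/8)/80 = 8.2, against 100/33.96 = 2.9 (ratio 2.8). With all 80 subjects followed for 168 days and four events, both formulas give 10.9.

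These figures start follow-up at Visit 6. SAP 7.10.1 counts from Visit 5, which may be up to 14 days earlier. Adding 14 days for the other 79 subjects gives 33.85 + 79 × 14/365.25 = 36.9 patient-years, which leaves the picture the same.

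**Drop-out unrelated to events.** Given x, m has mean λx/12, so 12m/x has mean λ and the SAP statistic is unbiased. With a common Poisson rate, its variance relative to the person-time rate is about mean(x) × mean(1/x). Assume exit times for 15% of subjects that are uniform between a floor of f days and 168 days. Then mean(x) = 0.85 × 168 + 0.15 × (168 + f)/2, and mean(1/x) = 0.85/168 + 0.15 × ln(168/f)/(168 − f).

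| f (days) | mean(x) | mean(1/x) | Variance ratio |
|---|---|---|---|
| 14 | 156.45 | 0.00748 | 1.17 |
| 7 | 155.93 | 0.00802 | 1.25 |
| 1 | 155.48 | 0.00966 | 1.50 |

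Simulation at an assumed 20 per 100 patient-years agrees: both estimators average 20. The SAP figure exceeds 1.5 times the person-time rate in about 2.5–3% of arms and twice that rate in about 1%. Simulated variance ratios are unstable because the statistic is heavy-tailed. Repeated runs gave values from about 1.1 to 2.1, always above 1.

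**Exit prompted by events (assumed; the documents give no probability).** Simulation at 20 per 100 patient-years, with gamma-distributed rates (shape 0.5) and 12% background drop-out:

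| First events leading to exit | SAP mean, floor 14 / 7 / 1 days | SAP median |
|---|---|---|
| 5% | 22.1 / 22.9 / 24.5 | 20 |
| 10% | 24.5 / 25.4 / 29.7 | 22 |
| 25% | 30.7 / 33.9 / 43.3 | 26 |

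The person-time rate averages 19.6–20.0 throughout.

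**The case against.** The SAP prints its formula in full and says what the average represents, so the calculation is reproducible and the certain fault is the name. The tenfold case is improbable, since it needs the arm's only event to fall in someone leaving at half a month. When drop-out is unrelated to events, the ratio of the SAP figure to the person-time rate has a median near 0.94, and about 90% of arms lie between 0.89 and 1.29. Early leavers' event-free time is over-weighted along with their events, which is why the mean is right. Upward bias needs event-driven exit, and a biased comparison would also need that exit to differ by arm. The documents establish neither. The 3-day sensor rule would not be a suitable floor here: one event at 3 days would still add 100 × 121.75/80 = 152 per 100 patient-years. Finally, the endpoint is descriptive, and event totals by arm and drop-outs with reasons are reported.

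All of this stands as a limit on reach. It does not repair the mismatch between name and formula. Nor does any other section supply a minimum x or a person-time rate. Protocol F.7 asks subjects who stop for safety reasons to be followed, but outside the study, so that does not lengthen x.

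**Conclusion.** The concern holds. As written, the rule in SAP 7.10.1 does not produce the quantity it names, and nothing limits the influence of very short follow-up. This should be fixed.

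The size depends on who has the events. It is usually modest, but a single event in an early leaver can multiply the reported rate several times when events are few. Without event-driven exit the cost is lost precision, with variance roughly 17–50% higher under the closed form above. With event-driven exit the statistic is biased upward. The event rates, exit times, heterogeneity and exit probabilities are all assumptions. Raw counts by arm are unaffected. The endpoint lies outside the test hierarchy in SAP 7.5, so the primary conclusion does not change.

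**What to change.** Replace the formula in SAP 7.10.1 with, for each arm: 100 × (total severe hypoglycemic events in the study phase) / (total study-phase patient-years), with follow-up from Visit 5 to Visit 15 or exit. Report the patient-years beside the event count.

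Add a 95% confidence interval that allows for repeated events in a subject, for example a subject-level bootstrap or a Poisson model with robust variance. Use an exact Poisson interval if there are only one or two events. A rate ratio from a model with log follow-up as offset is optional, if event numbers allow.

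If the mean of individual rates is kept, make it secondary, state a minimum x, and do not call it a crude incidence rate.

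The cost is one formula in the SAP and a few lines of code, with no new data. The interval will be wide if events are few.
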